**Table 5-5 Prohibited treatment**

Prohibited treatments	Prohibition 1/ Washout period before randomization 	Action to be taken
Biologic drugs directly targeting IL-17 or IL-17 receptor*	Never	Discontinue s.c. study treatment
Any cell-depleting therapies including but not limited to anti-CD20 or investigational agents (e.g. anti-CD3, anti-CD4, anti-CD5 or anti-CD19*)	Never	Discontinue s.c. study treatment
Tofacitinib or baricitinib	Never	Discontinue s.c. study treatment
Leflunomide	8 weeks	Discontinue s.c. study treatment
Leflunomide with cholestyramine washout	4 weeks	Discontinue s.c. study treatment
Other cDMARDs (except MTX if taken as outlined in 5.5.7.1)	4 weeks	Discontinue s.c. study treatment
Biological agent including but not limited to tocilizumab, sirukumab, abatacept or TNF $\alpha$ inhibitors (infliximab, adalimumab, etanercept, certolizumab, golimumab, )	Never	Discontinue s.c. study treatment
Intravenous immunoglobulins or plasmapheresis	8 weeks	Discontinuation s.c. study treatment may be required on a case by case basis.
Cyclophosphamide, tacrolimus or everolimus	6 months	Discontinue s.c. study treatment
Hydroxychloroquine, cyclosporine A, azathioprine, sulfasalazine or mycophenolate mofetil	4 weeks	Discontinue s.c. study treatment
Alkylating agents, except for cyclophosphamide	Never	Discontinue s.c. study treatment
Additional systemic glucocorticoid therapy	At Baseline, patients shall be able to adhere to the taper regimen	Patient enters ESCAPE
High potency opioid analgesics (except for PRN use; patients have to refrain from any intake during at least 24 hours before a visit)	2 weeks	Discontinuation of s.c. study treatment may be required on a case by case basis.
Any investigational treatment other than study medication or participation in any interventional trial	4 weeks or 5 half-lives (whichever is longer)	Discontinue s.c. study treatment
Live vaccinations	6 weeks	If administered due to a medical urgency, s.c. study treatment should be interrupted for 4 months. If administered not for a medical

Prohibited treatments	Prohibition 1/ Washout period before randomization 	Action to be taken
		urgency then s.c. study treatment should be discontinued

Abbreviations: DMARDs: disease modifying anti-rheumatic drugs MTX: methotrexate,

 Never = medication is prohibited from any time point prior to study start and up to and including follow-up visit.

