### **9.5 Analysis of secondary variables**

#### **9.5.1 Efficacy variables**

The following secondary efficacy endpoints for this study will be analyzed for the FAS:

- Remission rate at Week 12
- Time to first GCA flare after remission (up to Week 52)
- Total cumulative prednisolone dose over 28 Weeks and 52 Weeks
- Proportion of GCA patients in sustained remission at Week 52
  - Definition of remission: absence of flare.
  - Definition of sustained remission: patients without flare until Week 52 and in adherence to the protocol prednisolone taper regimen + prednisolone-free phase from Week 27 onwards
  - Definition of flare: determined by the investigator and defined as the recurrence after remission of signs or symptoms of GCA and/or erythrocyte sedimentation rate (ESR)  $\geq 30$  mm/hr and/or CRP  $\geq 10$  mg/L attributable to GCA
- Proportion of patients on prednisolone dose  $\leq 5$  mg/day at Week 19, Week 28 and Week 52

- Change from Baseline PGA at Week 4, 8, 12, 16, 20, 24, 28, 36, 44 and 52
- Change from Baseline PhGA at Week 4, 8, 12, 16, 20, 24, 28, 36, 44 and 52
- Change from Baseline FACIT-Fatigue at Week 4, 8, 12, 16, 20, 24, 28, 36, 44 and 52
- Change from Baseline SF-36 at Week 4, 8, 12, 16, 20, 24, 28, 36, 44 and 52
- Change from Baseline EQ-5D at Week 4, 8, 12, 16, 20, 24, 28, 36, 44 and 52
- Change from Baseline CRP at Week 4, 8, 12, 16, 20, 24, 28, 32, 36, 40, 44, 48 and 52
- Change from Baseline ESR at Week 4, 8, 12, 16, 20, 24, 28, 32, 36, 40, 44, 48 and 52

Similar to the primary endpoint methodology, the posterior distributions for the estimate of the OR, RD, and RR will be derived by sampling from the posterior distributions of the remission response rates at Week 12 of secukinumab and placebo. The prior distribution for the remission response rates at Week 12 for both treatment groups will be a Beta distribution with parameters 1/2 and 1/2, i.e. Beta (1/2, 1/2). The associated median and 95% credibility interval will be presented. Patients that withdrew from the study or entered “escape” therapy will be classified as non-responders from the point of withdrawal/escape onwards. Patients with a missing remission status at a particular time point will be classified as non-responders at that time point. In addition, the proportion of patients in remission over time will be summarized descriptively by visit and by treatment group.

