2.1.1 General definitions

2.1.1.1 Treatment

Study treatment

At Baseline, patients will be assigned to one of the following two arms in a 1:1 ratio:

- Group 1: secukinumab 300 mg subcutaneous (s.c.) + 26-week prednisolone taper regimen
- Group 2: placebo s.c. + 26-week prednisolone taper regimen

The study treatment is secukinumab 300 mg supplied in prefilled syringes (PFS) each containing 150 mg of secukinumab, or placebo supplied in PFS to match secukinumab dose.

Co-administered treatment

The co-administered treatment refers to prednisolone tablets for tapered oral administration (taper regimen from a dose of 25 mg to 60 mg at Baseline to 0 mg at Week 28). Prednisolone will be supplied as 1 mg, 5 mg, 10 mg, 20 mg tablets.

Note: Prednisolone may continue to be taken after the 26-week prednisolone taper regimen.

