22	Week 19	Study day 134 to Study day 140
23	Week 20	Study day 141 to Study day 147
24	Week 21	Study day 148 to Study day 154
25	Week 22	Study day 155 to Study day 161
26	Week 23	Study day 162 to Study day 168
27	Week 24	Study day 169 to Study day 175
28	Week 25	Study day 176 to Study day 182
29	Week 26	Study day 183 to Study day 189
30	Week 27	Study day 190 to Study day 196
31	Week 28	Study day 197 to Study day 203
32	Week 29	Study day 204 to Study day 210
33	Week 30	Study day 211 to Study day 217
34	Week 31	Study day 218 to Study day 224
35	Week 32	Study day 225 to Study day 231
36	Week 33	Study day 232 to Study day 238
37	Week 34	Study day 239 to Study day 245
38	Week 35	Study day 246 to Study day 252
39	Week 36	Study day 253 to Study day 259
40	Week 37	Study day 260 to Study day 266
41	Week 38	Study day 267 to Study day 273
42	Week 39	Study day 274 to Study day 280
43	Week 40	Study day 281 to Study day 287
44	Week 41	Study day 288 to Study day 294
45	Week 42	Study day 295 to Study day 301
46	Week 43	Study day 302 to Study day 308
47	Week 44	Study day 309 to Study day 315
48	Week 45	Study day 316 to Study day 322
49	Week 46	Study day 323 to Study day 329
50	Week 47	Study day 330 to Study day 336
51	Week 48	Study day 337 to Study day 343
52	Week 49	Study day 344 to Study day 350
53	Week 50	Study day 351 to Study day 357
54	Week 51	Study day 358 to Study day 364
55	Week 52	Study day 365 to Study day 371
56	Week 53	Study day 372 to Study day 379
57	Week 54	Study day 380 to Study day 386
58	Week 55	Study day 387 to Study day 393
59	Week 56	Study day 394 to Study day 400

Page 17 of 53

Timepoint	Week	Week definition
60	Week 57	Study day 401 to Study day 407
61	Week 58	Study day 408 to Study day 414
62	Week 59	Study day 415 to Study day 421
63	Week 60	Study day 422 to Study day 429

Note: Co-administered treatment refers to prednisolone taken for GCA. There should be a 26-week prednisolone taper regimen however a patient may take additional prednisolone over the 52-week treatment period.

2.2 **Analysis sets**

The following analysis sets will be used for the patients of interest:

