2.5.1 Primary endpoint

The primary endpoint is the proportion of GCA patients who are in sustained remission until Week 28.

The analysis of the primary variable will be based on the following estimand:

- Analysis set: FAS (for the patients of interest as outlined in Section 2.1)
- Variable of interest: Proportion of GCA patients who are in sustained remission until Week 28
 - Sustained remission: Patients without flare until Week 28 and in adherence to the protocol prednisolone taper regimen.

- Note: Flare is determined by the investigator and defined as the recurrence after remission of signs or symptoms of GCA and/or ESR \geq 30 mm/hr and/or CRP \geq 10 mg/L attributable to GCA.
- Adhere to prednisolone taper: Patients do not adhere to the prednisolone taper regimen if during the 26-week prednisolone taper regimen any of the following occur:
 - Patient does not take prednisolone medication for GCA for ≥ 6 consecutive days.
 - Patient takes prednisolone treatment for GCA for < 80% of the 26-week prednisolone taper regimen period.
 - Patient has received additional prednisolone for GCA to that stated in the taper regimen.

Note: This criteria (receiving additional prednisolone) does not apply to those patients in the "escape arm".

This means a patient is classified as receiving an additional prednisolone for GCA to that stated in the taper regimen if in the timeframe:

- [Week 0-Week 11] the patient's weekly dose is 20% over the stated dosage of prednisolone, or
- [Week 12-Week 26] the patient's weekly dose is 30% over the stated dosage of prednisolone.
- Patient received an additional corticosteroid to that stated in the taper regimen. Note: This will be based on the respective PD associated with this criteria.

Note: The final decision on whether the patient is non-adherent to the prednisolone taper will be confirmed by the blinded medical team on a by-patient basis in a Blind Data Review Meeting (BDRM) prior to CDBL. This decision will be documented in the associated BDRM minutes.

- Intervention effect: Effect between secukinumab versus placebo at Week 28 regardless of adherence to randomized treatment.
- Measure of intervention effect: Odds ratio (OR).

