2.7.2 Statistical hypothesis, model, and method of analysis

The proportion of patients in sustained remission until Week 52 (Yes, No) will be summarized descriptively for each treatment group. Note: Sustained remission at Week 52 refers to patients without flare until Week 52 and in adherence to the protocol prednisolone taper regimen. Flare is determined by the investigator and defined as the recurrence after remission of signs or symptoms of GCA and/or ESR \geq 30 mm/hr and/or CRP \geq 10 mg/L attributable to GCA. In addition, the reasons why a patient is determined to be a responder or non-responder to patients in sustained remission until Week 52 will be summarized.

The proportion of patients in remission (Yes, No) at each time point will be summarized descriptively for each treatment group. Note: Remission refers to the absence of flare. This summary table will only summarize remission information up to 4 weeks post last administration of study treatment.

The time to first GCA flare after remission (up to and including Week 52) will be summarized using Kaplan Meier curves. Descriptive statistics will also be provided for time to first GCA flare after remission in days (up to and including Week 52). This will also include information on follow-up. Follow-up is defined as:

• (Date of event or censoring – Baseline date) + 1 (regardless of censoring)

Total cumulative prednisolone dose from the first dose of co-administered prednisolone treatment to Weeks 26, Week 28, and 52 will be summarized over time by treatment group. Note: Prednisolone dose refers to prednisolone dose taken for GCA.

The number and percentage of patients on prednisolone dose \leq 5mg/day at Week 19, 28 and 52 will be summarized by treatment group. Note:

- Prednisolone dose refers to prednisolone dose taken for GCA.
- Prednisolone dose refers to the average co-administered prednisolone treatment in the week of interest.

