- Prednisolone dose for GCA will be based on the information collected on the "Dosage Administration Record-Prednisolone" eCRF. However as the prednisolone taper regimen is planned to be 26-weeks in duration, the Investigator is not required to enter daily prednisolone records on the "Dosage Administration Record-Prednisolone" eCRF post Week 26 unless the patient has taken additional prednisolone for GCA. Therefore if the patient is still in the study at the post Week 26 week of interest and has no prednisolone information in the "Dosage Administration Record-Prednisolone" eCRF for that week of interest the patient will be regarded as having 0 mg/day at that week of interest.

Descriptive summary statistics for the change as well as relative change from baseline of PhGA VAS to each study visit of interest will be presented for each treatment group. Change from baseline will only be summarized for patients with both baseline and post baseline values.

The analysis of the PRO secondary endpoints is detailed in Section 2.10.

Descriptive summary statistics for the change from baseline of CRP and ESR to each study visit of interest will be presented for each treatment group. Change from baseline will only be summarized for patients with both baseline and post baseline values. Further details are provided in Section 2.8.3. This analysis will also be presented for the following subgroups:

- Sustained remission until Week 28 (Yes, No)
- Sustained remission until Week 52 (Yes, No)

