2.7.3 Handling of missing values/censoring/discontinuations

For sustained remission until Week 52, patients will be classified as non-responders if they fulful any of the following:

- Do not achieve remission within 12 weeks of Baseline
 - Note: Remission refers to the absence of flare.
- Are in the "escape arm"
 - Note: This refers to the patient entering escape between Baseline and Week 52.
- Prematurely discontinue study treatment prior to Week 52
 - Note: Absence of flare is checked prior to study treatment administration.
- Do not have information to evaluate sustained remission response until Week 52

Patients receiving less than the full amount of prednisolone for GCA as required by the taper, e.g. due to missing tablets, will not be classified as non-responders with the exception of those who are classified as non-adherent to the prednisolone taper regimen (refer to Section 2.5.1 for definition of adherence to the prednisolone taper regimen). Note: The final decision on whether

the patient is non-adherent to the prednisolone taper will be confirmed by the blinded medical team on a by-patient basis in a BDRM prior to CDBL. This decision will be documented in the associated BDRM minutes.

For remission rate at Week 12, patients will be classified as non-responders if they fulfil any of the following:

- Prematurely discontinue study treatment
- Enter "escape" therapy

Note: Patients will be classified as non-responders for the above two scenarios from the point of withdrawal/escape onwards. Patients with a missing remission status at Week 12 will be classified as non-responders.

For time to first GCA flare after remission (up to and including Week 52), patients who:

- Prematurely discontinue study treatment prior to Week 52 will be censored at the time of premature discontinuation
- Complete treatment and do not have a flare will be censored at their last visit in the treatment phase

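### The SAP drops the prednisolone-free component from Week 52 sustained remission and adds under-dosing thresholds that count as non-response at Weeks 28 and 52; Section 4 identifies neither as a change

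*SAP*

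**What the plan says.** **Week 52 definition.** Protocol 9.5.1 counts a patient as in sustained remission at Week 52 if there is no flare and the patient is "in adherence to the protocol prednisolone taper regimen + prednisolone-free phase from Week 27 onwards". The protocol summary, Table 2-1 and section 6.3.2 give the same three parts. SAP 2.7.2 gives two: "Sustained remission at Week 52 refers to patients without flare until Week 52 and in adherence to the protocol prednisolone taper regimen". SAP 2.5.1 limits the adherence test to the taper: "Patients do not adhere to the prednisolone taper regimen if during the 26-week prednisolone taper regimen any of the following occur".

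**Escape.** For additional systemic glucocorticoid, protocol Table 5-5 gives the action "Patient enters ESCAPE". SAP 2.7.3 makes patients in escape non-responders for Week 52 and notes: "This refers to the patient entering escape between Baseline and Week 52".

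**Prednisolone after the taper.** SAP 2.1.1.1 notes: "Prednisolone may continue to be taken after the 26-week prednisolone taper regimen". The note to SAP Table 2-2 says that "a patient may take additional prednisolone over the 52-week treatment period". SAP 2.7.2 does not require dosing entries after Week 26 "unless the patient has taken additional prednisolone for GCA".

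**Under-dosing.** Protocol 5.2, 9.4.3 and 9.5.1 say that patients who take less than the full taper amount are not made non-responders for that reason. Protocol 3.1 says the same, with a proviso for other non-response criteria. SAP 2.5.1 lists 6 or more consecutive days without prednisolone, and intake for less than 80% of the taper period, as non-adherence. SAP 2.5.3 and 2.7.3 then except non-adherent patients from the protection. A blinded team confirms each case before database lock.

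**Declared changes.** SAP Section 4 has three entries: the baseline-dose subgroup cut, removal of adherence wording described as redundant, and timing from Baseline instead of from clinical remission.

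**The concern.** Week 52 was added to see whether remission holds without prednisolone; protocol 3.3 describes the period from Week 27 that way. A definition that stops testing prednisolone use when the taper ends does not by itself check this. A patient kept flare-free by prednisolone after Week 26 could count as a success.

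The under-dosing thresholds work in the opposite direction and reach the primary endpoint. A flare-free patient who took less prednisolone than planned can be a failure under the SAP and a success under the protocol. In an arm of about 25, a few such patients matter to the estimate and possibly to the GO criteria in SAP 2.5.2.

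A reader who relies on Section 4 to learn what changed would not learn of either difference. Section 4 does print the two-part definition, but as the existing rule.

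**Working it through.** **1. Week 52 components side by side**

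| Component | Protocol 9.5.1 | SAP 2.7.2 / 2.7.3 |
|---|---|---|
| No flare to Week 52 | required | required |
| Taper adherence | required | required, tested only during the taper |
| Prednisolone-free from Week 27 | required | absent |
| Escape before Week 52 | non-response | non-response |

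SAP Table 2-2 ends Week 26 on Day 189 and starts Week 27 on Day 190. The Week 52 target day in Table 2-1 is 365. Days outside the adherence test: 365 − 190 + 1 = 176.

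A patient who takes prednisolone for GCA in those 176 days can fall into one of three groups:
- flare recorded: non-responder under both documents;
- escape recorded: non-responder under both documents;
- neither recorded: fails the protocol's third component, but meets no non-response criterion in SAP 2.7.3.

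Only the third group is classified differently. No SAP rule derives escape or non-response from a dosing record after Week 26.

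**2. Reach of the under-dosing thresholds**

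The SAP does not give the taper period in days. It could be 26 × 7 = 182 days, or 189 days (Weeks 0 to 26 in Table 2-2). I assume that the 80% rule counts days.

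| | 182 days | 189 days |
|---|---|---|
| Days taken after one 6-day gap | 176/182 = 96.7% | 183/189 = 96.8% |
| 80% of the period | 145.6 days | 151.2 days |
| Missed days at which the 80% rule fails | 37 (145 left) | 38 (151 left) |

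The 6-day rule can therefore fail a patient who took prednisolone on nearly 97% of days.

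The smallest dose shortfall that can trigger it comes from 7 days per row, Weeks 0 to 26:
- Table 5-4 from 25 mg: 7 × (25+22+21+20+19+18+17+16 + 116) = 7 × 274 = 1,918 mg.
- Table 5-3 from 60 mg: 7 × (60+55+50+45+35+30+25+20 + 116) = 7 × 436 = 3,052 mg.
- Here 116 is the sum of the common rows, Weeks 8 to 26.
- Six missed days at 1 mg in Week 26 = 6 mg: 6/1,918 = 0.31%; 6/3,052 = 0.20%.

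This is the extreme case, chosen to show how little under-dosing the rule can act on. It is not a typical one.

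**3. What one patient is worth**

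One patient in 25 is 1/25 = 4 percentage points. For the primary endpoint, use the SAP priors: Beta(0.5, 0.5) for secukinumab and Beta(10, 43) for placebo. With 4/25 placebo responders, the posteriors are Beta(0.5 + x, 25.5 − x) and Beta(14, 64).

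| Secukinumab responders x of 25 | P(RD > 0.22) |
|---|---|
| 14 | 0.93 |
| 13 | 0.87 |
| 12 | 0.78 |
| 11 | 0.65 |
| 10 | 0.51 |
| 9 | 0.36 |

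The GO criterion needs at least 0.50, so the result changes between 10 and 9 responders. At the expected 14 responders, one reclassified patient changes nothing. These responder counts are illustrations, not predictions.

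**The case against.** **The Week 52 gap may be almost empty.** Protocol 5.5.7.1 permits no additional prednisolone. Flare, inability to adhere, and additional systemic glucocorticoid all lead to escape, which SAP 2.7.3 counts as failure. The SAP notes on prednisolone after the taper may describe only escape patients. This largely stands: the two definitions differ only if escape goes unrecorded. What remains is that classification then depends on a site recording escape, although the dosing form captures the drug itself. The protocol kept the third component alongside its escape rule.

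**The thresholds may only specify an undefined term.** The protocol requires taper adherence but sets no lower limit, so on a literal reading a patient who took almost nothing could count as adherent. Protocol 3.1 has its proviso, the SAP introduction says that it adds specifications, and the decision is blinded, made patient by patient and minuted. This is a fair reason to want a threshold. It does not remove the conflict: three protocol sections exempt under-dosing without the proviso, the proviso gives no threshold, and the only non-adherence described in protocol 3.1 is additional corticosteroid.

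**Much would be visible anyway.** The SAP summarises reasons for responder status at Week 28 (2.5.4) and Week 52 (2.7.2), lists prednisolone data for non-adherent patients (2.4.1), and tabulates cumulative dose and use at or below 5 mg/day. Patients failed for under-dosing would show. These outputs do not reclassify anyone, and a patient missed at Week 52 would appear as a responder.

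**Conclusion.** Both differences are in the text and should be resolved. They are of different weight.

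The Week 52 omission is a real but narrow gap in a secondary endpoint that the SAP only summarises descriptively and that is outside the GO criteria. A reader might infer that patients on continuing prednisolone would generally be counted as Week 52 successes, or that the SAP reports a different endpoint altogether. The documents do not support that, because the escape rule should remove most such patients.

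The under-dosing thresholds matter more because they also act on the primary endpoint. A reader might infer that any missed tablet makes a patient a failure. That is also not supported: the SAP keeps the exemption below its thresholds, and each case needs blinded confirmation.

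The number of patients affected by either difference is unknown, and so is the direction of any bias between arms. Each patient is 4 points, assuming 25 per arm. The GO result would be sensitive to one patient only near the threshold, about 10 secukinumab responders if placebo has 4 of 25.

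**What to change.** 1. In SAP 2.7.2 and 2.7.3, add that a Week 52 responder must also have no non-zero prednisolone dose for GCA on the Dosage Administration Record-Prednisolone eCRF from Week 27 (Study Day 190) to the Week 52 assessment. The word non-zero is needed because SAP 2.1.1.2 and 2.1.1.3 allow recorded doses of 0. Taper tablets carried past Day 189 by shifted visits go to the blinded review.

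2. Reconcile the under-dosing rule between protocol and SAP. Report the Week 28 and Week 52 results under the protocol's rule as well as under the 6-day/80% rule. State in Section 4 which is primary and why, and give the 80% denominator in days.

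3. If the Week 52 component is left out on purpose, Section 4 should say that it was dropped.

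The cost is SAP wording, one extra derivation and a second set of response tables. No new data are needed, since prednisolone for GCA after Week 26 is already to be entered. The Week 52 response rate may be slightly lower, and the blinded review gains the carried-over tablets.
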